### OTHER EMERGENCY TELEPHONE NUMBERS

## CLINICAL TRIAL SUMMARY

COMPOUND: alirocumab	STUDY No: LPS14245
TITLE	A Multi-Country, Multicenter, Single-Arm, Open-Label Study to Document the Safety, Tolerability and Effect of Alirocumab on atherogenic lipoproteins in High Cardio-Vascular Risk Patients With Severe Hypercholesterolemia Not Adequately Controlled With Conventional Lipid-Modifying Therapies.
INVESTIGATOR/TRIAL LOCATION	Europe & Canada.
PHASE OF DEVELOPMENT	Phase IIIb.
STUDY OBJECTIVE(S)	
Primary objective
 

• To provide patients with severe hypercholesterolemia at risk for subsequent cardiovascular (CV) events and not adequately controlled with currently available lipid modifying therapy (LMT) access to alirocumab ahead of commercial availability and to document the overall safety and tolerability of alirocumab in this patient population.

 
Secondary objective(s)
 

• To document the effect of alirocumab on low-density lipoprotein cholesterol (LDL-C) levels as well as non-high-density lipoprotein cholesterol (non-HDL-C), total cholesterol (total-C), high-density lipoprotein cholesterol (HDL-C), and triglyceride (TG) levels after 12 weeks of treatment.

• To document patient's acceptability of self-injection (Self Injection Assessment Questionnaire, SIAQ).

STUDY DESIGN	
This study will be conducted as a multi-country, multi-center prospective, single arm, open-label, phase IIIb clinical trial.
 
After enrollment, patients will receive study treatment alirocumab 150 mg subcutaneous (SC) once every 2 weeks (Q2W) or 75 mg subcutaneous (SC) Q2W. During the study, the dose may be adjusted according to the investigator, based on treatment response. Alirocumab will be administered on top of stable maximally tolerated statin therapy <math>\pm</math> other LMTs.
 
The study consists of:
 

• A screening period of up to 3 weeks, including an intermediate visit during which the patient or another designated person (such as spouse, relative, etc) will be trained to self-inject/inject.

• An open-label treatment period with alirocumab of at least 12 weeks and until the product becomes commercially available and reimbursed. However, the open label treatment period will not exceed 30 months.

• An end-of-study visit will take place at least 14 days after the last treatment injection.

 
Patients should be on a stable diet (NCEP-ATPIII TLC diet or equivalent) throughout the entire study duration from screening to the end of the study treatment.
 
Statin dose and dose regimen as well as dose and dose regimen of other LMTs (if applicable) should be stable throughout the whole study duration including the screening period.
 
Nevertheless, modification of LMT is allowed under certain conditions after enrollment as described in Section 8.

STUDY POPULATION	Inclusion Criteria:
Main selection criteria	

• Signed written informed consent.

• Age <math>\geq 18</math> years or legal age of majority at screening visit.

• Either A, B, C, D or E below and not adequately controlled with a maximally tolerated dose of statin* with or without other LMT, all at stable doses for at least 4 weeks prior to the screening visit (Week -3):

• A- Patients suffering from heterozygous familial hypercholesterolemia (heFH) with LDL-C concentrations <math>\geq 160</math> mg/dL (4.14 mmol/L) despite treatment.

• B- Patients suffering from heFH with LDL-C concentrations <math>\geq 130</math> mg/dL (3.36 mmol/L) despite treatment and two or more CV risk factors among this list :

- LDL-C <math>> 250</math> mg/dL (6.46 mmol/L) at the time of the familial hypercholesterolemia (FH) diagnosis (before treatment),

- Family history of premature-onset coronary heart disease (CHD) (first-degree male relative with onset before age 55 years; first-degree female relative with onset before age 65 years),

- Metabolic syndrome (cf. definition),

- HDL-C <math>< 40</math> mg/dL (1.03 mmol/L),

- Hypertension (BP <math>> 140/90</math> mmHg or drug treatment),

- Lipoprotein a [Lp(a)] <math>\geq 50</math> mg/dL (1.78 <math>\mu</math>mol/L),

- Tendon xanthoma.

• C- Patients suffering from heFH with LDL-C concentrations <math>\geq 130</math> mg/dL (3.36 mmol/L) despite treatment and one of the following characteristics:

- Established CHD or other CVD (history of acute myocardial infarction, ischemic stroke, peripheral arterial disease, coronary or peripheral arterial revascularization, stable or unstable angina, transient ischemic attack, carotid artery stenosis <math>\geq 50\%</math>, aortic abdominal aneurysm),

- Drug treated type 2 diabetes mellitus or type 1 with target organ damage,

- Family history of first or second degree relative with very premature onset CHD (first or second degree male relative onset before age 45; first or second degree female relative onset before age 55).

• D- Non-FH patients suffering from established CHD or other CVD (history of acute myocardial infarction (MI), ischemic stroke, peripheral arterial disease (PAD), coronary or peripheral arterial revascularization, stable or unstable angina, transient ischemic attack (TIA), carotid artery stenosis <math>\geq 50\%</math>, aortic abdominal aneurysm) and with LDL cholesterol concentrations <math>\geq 130</math> mg/dL (3.36 mmol/L).

• E- Patients suffering from progressive cardiovascular disease [coronary artery disease, or peripheral arterial occlusive disease or cerebrovascular disease as documented clinically or by imaging techniques, with a subsequent CV event (acute MI, ischemic stroke, ischemia driven revascularization, unstable angina, TIA) occurring despite stable doses of maximally tolerated LMT] with LDL cholesterol concentrations <math>\geq 100</math> mg/dL (2.59 mmol/L).


	
Note:
 
* Definition of maximally tolerated dose (any of the following are acceptable):
 

• Rosuvastatin 20 mg or 40 mg daily.

• Atorvastatin 40 mg or 80 mg daily.

• Simvastatin 80 mg daily (if already on this dose for >1 year).

• Patients not able to be on any of the above statin doses should be treated with the dose of atorvastatin, rosuvastatin or simvastatin which is considered appropriate for the patient as per the investigator's judgment or concerns.

 
NB: in exceptional and well documented cases described in Exclusion criteria E04, another statin regimen may be used.
 

• Some examples of acceptable reasons for a patient taking a lower statin dose include, but are not limited to: adverse effects on higher doses, advanced age, low body mass index, concomitant medications, and co-morbid conditions such as impaired glucose tolerance /impaired fasting glucose. The reason(s) will need to be documented in the case report form.

Total expected number of patients	It is anticipated that approximately 1300 patients will be enrolled in this study.

[figure not shown]
STUDY TREATMENT(s)	
Investigational medicinal product(s)	Alirocumab. Prefilled pens containing alirocumab 75 mg/mL or 150mg/mL.
Formulation	Sterile alirocumab drug product supplied at a concentration of 75 mg/mL and 150 mg/mL in histidine, pH 6.0, polysorbate 20, and sucrose, both as 1 mL volume in a pre-filled pen.
Route(s) of administration	Subcutaneous (SC) injections in the abdomen, thigh or outer area of upper arm.
Dose regimen	The dose is 75 mg or 150 mg administered subcutaneously once every 2 weeks (Q2W). The dose selection should be based on individual patient characteristics and goal of therapy. The dose can be adjusted based on treatment response.
Injection for training	Placebo for alirocumab.
Formulation	Sterile solution consisting of histidine, pH 6.0, polysorbate 20, and sucrose, as 1 mL volume in a pre-filled pen.
Route of administration	Subcutaneous (SC) injections in the abdomen, thigh or outer area of upper arm.
ENDPOINT(S)	
Primary endpoint: Safety parameters (adverse events, adverse events of special interest, laboratory data, product complaints and vital signs) assessed throughout the study.
 
Secondary endpoint(s): Patients' acceptability of self-injection (Self Injection Assessment Questionnaire). Among other endpoints of interest, see Section 9.2.2:
 
 
• Proportion of patients reaching calculated LDL-C <100 mg/dL (2.59mmol/L) at Week 12.
 
• Proportion of patients reaching calculated LDL-C <70 mg/dL (1.81mmol/L) at Week 12.
 
• Proportion of patients with LDL-C <70 mg/dL (1.81 mmol/L) and/or ≥50% reduction from baseline in LDL-C (if LDL-C ≥70 mg/dL [(1.81 mmol/L)]) at Week 12.
 
• Percent changes from baseline in LDL-C as well as non-HDL-C, total-C, HDL-C, and TG levels after 12 weeks of treatment.
 
 
All endpoints will be defined in the SAP.

ASSESSMENT SCHEDULE	
Patient's assessments in the screening period:
 
 
• On-site visits: Week -3 (screening visit), Week -1 (injection training visit if needed).
 
 
Patient's assessments in the treatment period:
 
 
• On-site visits: Week 0 (inclusion visit), Week 4, Week 8, Week 12, Week 24, Week 48, then every 12 weeks until end of treatment (EOT/EOS).
 
• Phone calls: Week 2 and Week 18.
 
• Dispensation visits every 12 Weeks after Week 24.
 

STATISTICAL CONSIDERATIONS	
Sample size determination: No formal sample size calculation is performed. The table below displays the 95% Confidence intervals (95%CI) associated to a variety of adverse event rates for a targeted sample size of 1300 patients.
 

Adverse event rates	10%	20%	30%	40%	50%	

95%CI	[8.4%; 11.6%]	[17.8%; 22.2%]	[27.5%; 32.5%]	[37.3%; 42.7%]	[47.3%; 52.7%]	

 
For a rare non observed event, by using the rule of three, it can be estimated that the upper limit of the 95% confidence interval of the event rate is approximately 0.23% (1 per 433).
 
Analysis population: Safety population: all enrolled patients who actually received at least one dose or partial dose of alirocumab.
 
Efficacy population: Modified Intend To Treat population (mITT): all enrolled patients who received at least one dose or partial dose of alirocumab, with a baseline LDL-C value available and with at least one on-treatment LDL-C measurement during the efficacy treatment period.
 
Primary analysis: Safety analysis (adverse events, laboratory, product complaints and vital signs) will be performed on the safety population. Only descriptive summaries will be provided. The number of adverse events (AEs) during the study will be displayed. Adverse event incidence tables will present, by system organ class (SOC) high level group term (HLGT), high level term (HLT) and preferred term (PT), the number (n) and percentage (%) of patients experiencing an AE.
 
Secondary analysis: The effects of alirocumab will be documented by the proportion of patients reaching calculated LDL-C <100 mg/dL (2.59 mmol/L) at Week 12, the proportion of patients reaching calculated LDL-C < 70 mg/dL (1.81 mmol/L) at Week 12 as well as by values and percent changes from baseline in LDL-C, non-HDL-C, total-C, HDL-C, and TG levels after 12 weeks of treatment and at other time points. A descriptive analysis of the SIAQ will be done on the safety population. More details regarding statistical analyses will be provided in the SAP.
	Adverse event rates	10%	20%	30%	40%	50%	95%CI	[8.4%; 11.6%]	[17.8%; 22.2%]	[27.5%; 32.5%]	[37.3%; 42.7%]	[47.3%; 52.7%]
Adverse event rates	10%	20%	30%	40%	50%								
95%CI	[8.4%; 11.6%]	[17.8%; 22.2%]	[27.5%; 32.5%]	[37.3%; 42.7%]	[47.3%; 52.7%]								
DURATION OF STUDY (PER PATIENT)	
The study duration includes up to 3 weeks of screening period, a minimum of 12 weeks and up to a maximum 30 months of open label study treatment period and at least 2 weeks after the last study treatment injection.
 
In each country, patient recruitment will end when alirocumab becomes commercially available (ie, accessible to the patient as per each country regulation) and reimbursed. In this case, study treatment can be switched to the commercial product once the patient has completed the minimum of 12 weeks of study treatment.
												

STUDY COMMITTEES	Steering Committee:  Yes  No
	Data Monitoring Committee:  Yes  No
	Adjudication Committee:  Yes  No

## 1 FLOW CHART

### 1.1 GRAPHICAL STUDY DESIGN

## 1.2 STUDY FLOW CHART

Study time points	Screening period		Inclusion visit	Study Treatment														
	W-3 (D-21 to -8) Screening visit	W-1 D-7 Injection training visit * (optional)		W0 D1	W2 D15 ■	W4 D29	W8 D57	W12 D85	W18 D127 ■	W24 D169	W36 ** D253	W48 D337	W60 ** D421	W72 D505	W84 ** D589	W96 D673	W108 ** D757	EOT/EOS Week 120 *** Day 841 +2 weeks after last injection
Visit number	V1	V2	V3	V4	V5	V6	V7	V8	V9	V10	V11	V12	V13	V14	V15	V16	V17	
Visit windows			+3	±3	±3	±3	±3	±5	±5	±7	±7	±7	±7	±7	±7	±7	+7	
Inclusion and exclusion criteria	✓		✓															
Eligibility confirmation and enrollment			✓															
Informed consent form	✓																	
Demography	✓																	
Medical history	✓																	
Prior/Concomitant medication/LMT a	✓		✓	✓	✓	✓	✓	✓	✓	✓	✓	✓	✓	✓	✓	✓	✓	
Review of diet	✓					✓	✓	✓		✓		✓		✓		✓		
Patient diary: dispensation / review / collection			✓		✓	✓	✓		✓	✓	✓	✓	✓	✓	✓	✓	✓	
Injection training		✓																
SIAQ PRE		✓																
SIAQ POST			✓		✓	✓	✓	✓		✓		✓		✓		✓		
Physical examination b	✓		✓		✓	✓	✓	✓		✓		✓		✓		✓	✓	

Study time points	Screening period		Inclusion visit	Study Treatment														
	W-3 (D-21 to -8) Screening visit	W-1 D-7 Injection training visit * (optional)		W0 D1	W2 D15 📞	W4 D29	W8 D57	W12 D85	W18 D127 📞	W24 D169	W36 ** D253	W48 D337	W60 ** D421	W72 D505	W84 ** D589	W96 D673	W108 ** D757	EOT/EOS Week 120 *** Day 841 +2 weeks after last injection
Visit number	V1	V2	V3	V4	V5	V6	V7	V8	V9	V10	V11	V12	V13	V14	V15	V16	V17	
Visit windows			+3	±3	±3	±3	±3	±5	±5	±7	±7	±7	±7	±7	±7	±7	+7	
Hematology and biochemistry c d	✓				✓		✓		✓		✓		✓		✓		✓	✓j
HbA1c	✓						✓		✓		✓		✓		✓		✓	✓j
Lipid profile e	✓				✓	✓	✓		✓		✓		✓		✓		✓	✓j
Urinalysis	✓			✓			✓											✓
Liver panel f	✓				✓	✓	✓		✓		✓		✓		✓		✓	✓j
Hepatitis B and C serology	✓																	✓l
Telephone assessment g 📞					✓				✓									
Study treatment dispensation				✓		✓k	✓k	✓		✓	✓	✓	✓	✓	✓	✓	✓	
Compliance check i					✓	✓	✓		✓	✓	✓	✓	✓	✓	✓	✓	✓	
Study treatment administration g				✓	← →													
Pregnancy test (women of childbearing potential)	✓ m		✓ n															✓ n
+AE/SAE recording h	←								✓									→

\* Injection training can also be performed during the screening or the inclusion visit.

\*\* Dispensation visits.

\*\*\* Those patients with unresolved SAE/AESI at the EOT/EOS visit will be followed up by the investigator for as long as medically indicated, but without further recording in the eCRF

a. Prior and concomitant medications started within 4 weeks before screening visit, lipid lowering therapies, antihypertensive medications, AEs/SAEs corrective therapies.

Study time points	Screening period		Inclusion visit	Study Treatment														
	W-3 (D-21 to -8) Screening visit	W-1 D-7 Injection training visit * (optional)		W2 D15 📞	W4 D29	W8 D57	W12 D85	W18 D127 📞	W24 D169	W36 ** D253	W48 D337	W60 ** D421	W72 D505	W84 ** D589	W96 D673	W108 ** D757	EOT/EOS Week 120 *** Day 841 +2 weeks after last injection	
Visit number	V1	V2	V3	V4	V5	V6	V7	V8	V9	V10	V11	V12	V13	V14	V15	V16	V17	
Visit windows			+3	±3	±3	±3	±3	±5	±5	±7	±7	±7	±7	±7	±7	±7	+7	
b.	Physical examination and vital signs: height (only at screening), weight, HR, BP.																	
c.	Hematology: hemoglobin, RBC, Hb, Hematocrit, platelets, WBC count with differential blood count. Recent (1 week) lab result may be used instead. In case of unexpected or aberrant value a retest must be done before inclusion.																	
d.	Biochemistry: glucose, urea, calculated creatinine clearance, creatinine and eGFR using MDRD study equation, total CPK, sodium, potassium, chloride, bicarbonate, calcium, phosphorus, uric acid, total protein, LDH, albumin, GGT, Hepatitis C antibody (at screening, EOT/EOS and in case of transaminases elevation) to be confirmed by reflexive testing when positive, Hepatitis B antigen (screening only). Recent (1 week) lab result may be used instead. In case of unexpected or aberrant value a retest must be done before inclusion.																	
e.	Lipid profile: Total Cholesterol, Triglycerides, Calculated LDL-C, HDL-C, non-HDL-C. Recent (1 week) lab result may be used instead. In case of unexpected or aberrant value a retest must be done before inclusion.																	
f.	Liver panel: SGOT (AST), SGPT (ALT), alkaline phosphatase, total bilirubin. Recent (1 week) lab result may be used instead.																	
g.	Dose regimen: alirocumab 75 mg/mL or 150 mg/mL, SC, Q2W for the entire study treatment duration. Depending on the clinical situation, alirocumab can be started at 75 mg or 150 mg administered once every 2 weeks. During the study, the dose may be adjusted according to the investigator, based on treatment response.																	
h.	Safety evaluation: Adverse Events (AEs), product complaints, regardless of seriousness or relationship to alirocumab treatment, will be collected from the time the patient signs the informed consent form up to the EOT/EOS visit																	
i.	Review patient diary and treatment kit +data collection on study treatment administration.																	
j.	Repeat lab only in case of abnormality at EOT/EOS.																	
k.	New kit dispensation only if needed as per lab results.																	
l.	Hepatitis C only.																	
m.	Serum pregnancy test.																	
n.	Urine pregnancy test.																	

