## **6.2 DURATION OF STUDY PARTICIPATION**

### **6.2.1 Duration of study participation for each patient**

The study duration includes up to 3 weeks of screening period, a minimum of 12 weeks and up to a maximum 30 months of open label study treatment period and at least 2 weeks after the last alirocumab injection.

In each country, patient recruitment will end when alirocumab becomes commercially available (ie, accessible to the patient as per each country regulation) and reimbursed. In this case, study treatment can be switched to the commercial product (or another LMT) once the patient has completed the minimum of 12 weeks of study treatment.

The end of the study per patient is the last protocol planned visit or the resolution/stabilization of all SAEs and adverse event of special interest (AESI), or death, whichever comes last.

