#### **10.4.2 General guidelines for reporting adverse events (and product complaints)**

- All AEs, regardless of seriousness or relationship to investigational medical product (IMP)/ non investigational medical product (NIMP), spanning from the signature of the informed consent form until the end of the study as defined by the protocol for that patient, are to be recorded on the corresponding page(s) or screen(s) of the CRF.
- All products complaints associated or not to an AE are to be recorded immediately on the corresponding products (study medical device) complaints pages and reported to local Complaint Service immediately (within 24 hours).

- Whenever possible, diagnosis or single syndrome should be reported instead of symptoms. The Investigator should specify the date of onset, intensity, action taken with respect to IMP, corrective treatment/therapy given, additional investigations performed, outcome, and his/her opinion as to whether there is a reasonable possibility that the AE was caused by the IMP or by the study procedure(s).
- The Investigator should take appropriate measures to follow all AEs until clinical recovery is complete and laboratory results have returned to normal, or until progression has been stabilized, or until death, in order to ensure the safety of the patients. This may imply that observations will continue beyond the last planned visit per protocol, and that additional investigations may be requested by the monitoring team up to as noticed by the Sponsor.
- Patients who experience an ongoing SAE or an AESI, at the prespecified study end-date, should be followed until resolution, stabilization, or death and related data will be collected. The duration of post study follow-up and reporting of AEs will be specified (eg, until recovery).
- When treatment is prematurely discontinued, the patient will have an EOT (=EOS) visit at least 2 weeks after the last study treatment injection unless there is an AE to be followed until final outcome and related data will be collected.
- Laboratory or vital signs are to be recorded as AEs only if:
  - Symptomatic and/or,
  - Requiring either corrective treatment or consultation, and/or,
  - Leading to IMP discontinuation or modification of dosing, and/or,
  - Fulfilling a seriousness criterion, and/or,
  - Defined as an AESI.

Instructions for AE reporting are summarized in [Appendix E](#).

- Adverse event (injection site reactions) recorded in patient's questionnaire:  

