##### ***Observation period***

For all enrolled patients, the period of safety observation starts from the time when the patient gives his/her informed consent and is divided into the following periods:

- The PRE-TREATMENT observation period is defined from the signed informed consent up to the first dose of alirocumab.
- The treatment-emergent adverse event (TEAE) period is defined as the time from the first injection of alirocumab up to the day of the last injection of alirocumab + 14 days.
- The POST-TREATMENT period will cover a period from the day after the end of the TEAE period up to the end of the study (defined as last protocol-planned visit or the resolution/stabilization of all SAEs and AEs with pre-specified monitoring as defined in protocol).

The on-study observation period is defined as the time from the day of first dose of alirocumab until the last protocol planned visit of the patient.

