#### **2.1.4.2 Deaths**

The deaths observation period is per the observation periods defined above.

- Death on-study: deaths occurring during the on-study observation period.
- Death on-treatment: deaths occurring during the TEAE period.
- Death post-study: deaths reported after the last planned protocol visit.

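### The flow chart stops eCRF entry for SAEs and AESIs still open at EOT/EOS while protocol 10.4.2 and 10.4.3 continue it, so a late fatal outcome can be missing from the table of TEAEs leading to death

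*Protocol*

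**What the plan says.** Three places in the protocol end recording at the final visit.

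- Section 1.2, footnote ***: SAEs and AESIs unresolved at EOT/EOS are followed by the investigator "for as long as medically indicated, but without further recording in the eCRF".
- Section 1.2, footnote h: AEs and product complaints "will be collected from the time the patient signs the informed consent form up to the EOT/EOS visit".
- Section 10.1.1, screening visit: AEs and SAEs are collected until a follow-up visit after study treatment.

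Other current text continues it.

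- Section 10.4.2, first bullet: all AEs from consent "until the end of the study as defined by the protocol for that patient, are to be recorded" in the CRF. Section 6.2.1 sets that per-patient end at "the last protocol planned visit or the resolution/stabilization of all SAEs and adverse event of special interest (AESI), or death, whichever comes last".
- Section 10.4.2, on patients with an SAE or AESI ongoing at the study end date: they "should be followed until resolution, stabilization, or death and related data will be collected".
- Section 10.4.3: later updates on an SAE go into the e-CRF, with no stop stated at EOT/EOS.

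SAP 2.1.4 runs the post-treatment period "up to the end of the study (defined as last protocol-planned visit or the resolution/stabilization of all SAEs" and AEs with pre-specified monitoring. SAP 2.1.4.1 collects AEs to the end of the safety observation period.

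SAP 2.4.5.1 includes TEAEs leading to death as a line in the TEAE overview. SAP 2.4.5.2 gives them their own table, identified by a death outcome that the investigator reports on the AE page of the case report form. For deaths by period, SAP 2.1.4.2 has "Death post-study: deaths reported after the last planned protocol visit", whereas protocol 9.1.1 counts a death as post-study only after the end of study defined in 6.2.1.

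**The concern.** Safety is the primary endpoint, and fatal TEAEs are among its least frequent and most closely read results. EOT/EOS falls 14 to 21 days after the last injection (protocol 10.1.2.5), so some treatment-emergent SAEs will have no final outcome by then. Whether that outcome reaches the analysis database depends on which part of the protocol the site follows. An omission can only lower the number of TEAEs leading to death. The study has one arm, so no comparator carries the same loss. It also has no adjudication or data monitoring committee that might recover the outcomes.

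**Working it through.** No figure in the plan is disputed. The check is a comparison of text, followed by an illustration of scale.

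**1. What each place says about recording after EOT/EOS**

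| Place | Names the CRF/eCRF? | Effect after EOT/EOS |
|---|---|---|
| Protocol 1.2, footnote *** | Yes | Recording stops |
| Protocol 1.2, footnote h | No | AE collection has ended |
| Protocol 10.1.1 | No | AE collection ends at a follow-up visit |
| Protocol 10.4.2, first bullet, with 6.2.1 | Yes (10.4.2) | Recording continues to the per-patient end of study |
| Protocol 10.4.2, ongoing SAE/AESI | No (data collected) | Collection continues |
| Protocol 10.4.3 | Yes | SAE updates continue |
| Protocol 6.2.1 alone; SAP 2.1.4 and 2.1.4.1 | No | Define periods only |

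The direct conflict is between footnote *** and sections 10.4.2 and 10.4.3. Section 6.2.1 matters because 10.4.2 refers to the per-patient end of study. The SAP passages matter because they assume a collection period that the flow chart cuts short.

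**2. One patient under both rules**

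The TEAE period ends 14 days after the last injection (protocol 9.1.1, SAP 2.1.4). EOT/EOS is no later than day 21. An SAE with onset on day 14 therefore has at most 21 − 14 = 7 days to reach a recordable outcome. Suppose it is open at EOT/EOS and the patient later dies of it.

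- Flow chart followed: the AE page keeps a non-fatal or unresolved outcome, and the patient is absent from the table of TEAEs leading to death.
- Sections 10.4.2 and 10.4.3 followed: the AE page shows death, and the patient is counted.

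**3. Outputs affected and not affected**

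- Affected: the overview line and table of TEAEs leading to death; final outcomes of SAEs and AESIs; possibly the post-study death count.
- Pregnancy shows the same gap without any death rate. It is an AESI for 70 days after the last dose and must be followed to its outcome (10.4.1.3), yet EOT/EOS can close recording 70 − 21 = 49 to 70 − 14 = 56 days earlier.
- Not affected: incidence of TEAEs, SAEs and AESIs with onset in the TEAE period; on-treatment deaths (to last injection + 14 days); on-study deaths (to the last planned visit).

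**4. Scale, as illustration only**

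Inputs: 7 of 1553 alirocumab patients had TEAEs leading to death in the long-term placebo-controlled study summarised in protocol section 4; planned N = 1300. The quoted 0.5% reproduces after rounding: 7/1553 = 0.45%. Expected count: 1300 × 7/1553 = 5.9, about 6. The share of such deaths falling after EOT/EOS is not given, so 0 to 3 missed is assumed (Clopper-Pearson 95% intervals).

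| Missed | Counted | Rate | 95% CI |
|---|---|---|---|
| 0 | 6 | 6/1300 = 0.46% | 0.17 to 1.00 |
| 1 | 5 | 5/1300 = 0.38% | 0.12 to 0.90 |
| 2 | 4 | 4/1300 = 0.31% | 0.08 to 0.79 |
| 3 | 3 | 3/1300 = 0.23% | 0.05 to 0.67 |

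**5. The boundary for post-study deaths**

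A patient who dies after EOT/EOS with an SAE still unresolved is post-study under SAP 2.1.4.2. Under protocol 9.1.1, read with 6.2.1, the patient was still in the study. The same death falls into different categories in the two documents.

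**The case against.** Several points on the other side are sound.

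- Section 10.4.2 is not a clean rule: it adds that the duration of post-study follow-up and reporting will be specified.
- A global amendment deliberately streamlined the end of study (SAP 1.5), so stopping eCRF entry may be intended. If so, 10.4.2 and 10.4.3 should say so, and the SAP needs a source other than the AE page for late fatal outcomes. It names none.
- Safeguards exist. Section 10.4.3 asks for further documentation of fatal or life-threatening SAEs within 7 days, Appendix K sends pregnancy information to the sponsor on its own form, and post-study deaths have their own line. These may bring the outcome to the sponsor, but they do not change what the planned table reads.
- All analyses are descriptive, so no test is at risk.

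A reader might infer more than the documents support.

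- That 6.2.1 and SAP 2.1.4 themselves require eCRF entry to continue. They define periods and do not mention the eCRF.
- That the primary safety results as a whole are biased. Incidence and deaths up to the last planned visit are not touched.
- That each late death lowers the fatal count by a known percentage. Any such figure is 1 divided by an assumed count, and its source study had at least 52 weeks of data for patients continuing treatment, against 12 weeks to 30 months of treatment here.
- That the SAP should adopt the 6.2.1 end of study as its death boundary. That wording includes death itself and takes whichever event is last, so read literally no death would be post-study.

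**Conclusion.** The contradiction is real, stands in current text and reaches a planned safety output. At sites following the flow chart, a treatment-emergent SAE open at EOT/EOS that later proves fatal would not appear among TEAEs leading to death. Final SAE and AESI outcomes, pregnancy outcomes and post-study deaths could also be recorded unevenly across sites. The direction of any error in the fatal count is known; its size is not, because the documents do not say how many SAEs are open at EOT/EOS or how many of those end in death. It could be zero. The fall from 0.46% to between 0.38% and 0.23% assumes that the earlier study's rate carries over and that one to three deaths are missed. With about 6 events expected on that assumption, even one omission is visible. The differing definitions of post-study death are a separate and smaller matter of labelling.

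**What to change.** 1. In footnote *** of section 1.2, delete the clause that ends eCRF recording.
2. Align footnote h and the AE collection end point in section 10.1.1 with 10.4.2 and 10.4.3. Changing footnote *** alone would leave both in conflict.
3. Require the outcome and outcome date of every SAE and AESI ongoing at EOT/EOS to be entered in the eCRF until resolution, stabilization or death, or until a stated data cutoff before database lock. A cutoff is needed because SAP section 4 plans the lock about 10 weeks after last patient last visit. State that later outcomes are taken from the safety database.
4. Use one boundary for post-study deaths in protocol 9.1.1 and SAP 2.1.4.2. The SAP's last planned visit is workable and applies alike to every patient.

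The cost is edits to three protocol places on AE collection, one definition to reconcile, a cutoff rule, and a small amount of data entry for patients whom sites already follow.
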